#### 17.4.2.12.2 Analysis

For each microorganism, the number and percentage with at least one positive result will be presented split by treatment arm, and a relative risk and 95% confidence interval calculated. Chi-squared tests (or if necessary Fisher's exact test) will be used to test for differences between treatment groups.

Secondly, for each microorganism: the number and percentage with at least one positive result during the treatment phase; and by 15 months will be presented split by treatment-arm. Of those that were followed up to  $T_{24}$ , and for each microorganism, the number and percentage with at least one positive result by  $T_{24}$  will be presented split by treatment-arm.

Chi-squared tests will be used to test for differences between treatment groups.

Other organisms detected will be listed as a frequency table split by treatment arm. Frequencies presented will be the number of children with at least one positive culture of the organism during the study.

#### 17.4.2.13 Cost per patient (from NHS perspective)

#### 17.4.2.13.1 Derivation

The derivation of this outcome will be described in the health economics analysis plan.

#### 17.4.2.13.2 Analysis

The analysis of this outcome will be described in the health economics analysis plan.

# 17.4.2.14 Incremental cost effectiveness ratio (cost per successfully treated patient, cost per QALY)

#### 17.4.2.14.1 Derivation

The derivation of this outcome will be described in the health economics analysis plan.

#### 17.4.2.14.2 Analysis

The analysis of this outcome will be described in the health economics analysis plan.

#### If the scheduled visit at $T_{15}$ does take place, we can derive:

A binary variable X measuring carer absenteeism from education/work during the first 15 months (from baseline to  $T_{15}$ ) will be derived as follows:

#### Form prepared: 20/06/2018 v1.0 for TORPEDO-CF Study

Page 41 of 47

X=1 if a participant had at least one day off work or missed at least one day of education during any follow-up visit (scheduled or unscheduled) taking place on or before the scheduled visit at T15 (FUPTOWVC='Yes' or FUPTOEVC='Yes' or UVPTOWVC ='Yes' or UVPTOEVC ='Yes')

X=0 otherwise

A length of time variable Y measuring carer days of absenteeism from education/work during the study (from baseline to  $T_{15}$ ) will be derived as follows:

Y = (FUPTOWVI + UVPTOWVI + FUPTOEWI + UVPTOEWI) x 7

+ (FUPTODVI + UVPTODVI + FUPTOEDI + UVPTOEDI) added up for all visits taking place after the scheduled visit on or before the scheduled visit at  $T_{15}$ 

If the scheduled visit at  $T_{15}$  does not take place, there is ambiguity as to whether carer burden reported at the next visit after  $T_{15}$  relates to pre or post  $T_{15}$  or both. The same methodology as given in 17.4.7.2.1 and 17.4.7.3.1 will be used to estimate whether the carer burden was likely to be pre  $T_{15}$  or after, and to interpolate an estimated number of days spent absent that can be attributed pre  $T_{15}$ .

#### 17.4.2.15.2 Analysis

This outcome will be presented in two ways. Firstly, whether carers have been absent from education or work or not during the first 15 months post randomisation, will be analysed using a relative risk, presented with a 95% confidence interval and a chi squared test. Secondly, the number of days spent absent from work or education will be presented as a median with 95% confidence interval for each treatment arm, together with the interquartile range, min and max. A Mann Whitney test will be used to detect differences in the distributions of carer burden between the two treatment groups.

#### 17.4.2.16 Participant burden (absenteeism from education or work)

#### 17.4.2.16.1 Derivation

This is the same as for carer burden (see 17.4.2.15.1 above), but with the absenteeism binary variable derived from variables FUTOEVC, FUTOWVC, UVTOEVC and UVTOWVC; and length of time away from education and work derived from the variables FUTOEWVI, FUTOEDVI, FUTOWDVI, UVTOEWVI, UVTOEDVI, UVTOWWVI, and UVTOWDVI.

#### 17.4.2.16.2 Analysis

The analysis is exactly the same as described in 17.4.2.15.2 above.

## **18 Missing Data and Withdrawals**

Explicit derivations above give methods for handling missing data and withdrawals regarding derivation of outcomes. Section 14.2 above describes how withdrawals will be reported.

## **19 Additional Analyses**

#### **19.1 Sensitivity analyses of to the primary outcome analysis**

#### 19.1.1 Withdrawn patients all classified as success

Derivation and analysis as in Section 17.4.1.1 and Section 17.4.1.2 but all patients who have been followed up past 3 months but not had a sample within the 15 month window will be assumed to have not had *P. Aeruginosa*.

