#### 17.4.1.1 Derivation

The CRF: *Microbiology Form* captures information on samples taken at all attended visits (scheduled and unscheduled). The variable MBDSTD gives the date the sample was taken, and the variable MBOC6C indicates that *P. aeruginosa* was cultured if it is selected (MBOC6C = "Pseudomonas aeruginosa").

Success: If there is no record of *P. aeruginosa* on a patient's microbiology CRF between 3 months and 15 months after treatment commencement.

Failure: If there is at least one record of *P. aeruginosa* on a patient's microbiology CRF between 3 months and 15 months after treatment commencement.

Any positive samp	Outcome		
<3 months	3-15 months	>15 months	
×	×	×	Success
×	×	✓	Success
✓	×	×	Success
✓	×	✓	Success
×	$\checkmark$	×	Fail
×	$\checkmark$	✓	Fail
✓	$\checkmark$	×	Fail
✓	$\checkmark$	$\checkmark$	Fail

To determine if a patient has eradicated *P. Aeruginosa* at 3 months, they must have a sample within 28 days either side of the expected 3 month visit date (treatment commencement date + 84 days) which is at least 2 days after the last date of any anti-pseudomonal treatment.

To determine if a patient has remained *P. Aeruginosa* free at 15 months, they must have either a positive sample within the primary outcome window (3-15 months) or they must have a sample within 28 days either side of the expected 15 month visit date (treatment commencement date + 420 days). Patients who have not regrown *P. Aeruginosa* and do not have a sample within the 15 month window (defined above) will not be included in the primary analysis. If a patient is withdrawn before 15 months of follow-up is completed, they will only be included in the primary outcome analysis if they have failed. If there is no evidence that they have failed prior to being withdrawn they will not be included in the primary analysis.

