#### 19.1.2 Withdrawn patients all classified as failure

Derivation and analysis as in Section 17.4.1.1 and Section 17.4.1.2 but all patients who have been followed up past 3 months but not had a sample within the 15 month window will be assumed to have had *P. Aeruginosa*.

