#### 19.1.3 Results of blind review

Derivation and analysis as in Section 17.4.1.1 and Section 17.4.1.2 but all patients that have been followed up for more than 15 months but not had a sample within the 15 month window will be included. These patients will be classified as success or failure based on the next sample that was taken following the 15 month window.

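### The missing-data sensitivity analyses of the primary outcome do not bound the effect of missing outcomes, and 19.1.1 and 19.1.3, as worded, can reclassify known failures

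*SAP*

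**What the plan says.** **Primary rule (SAP 17.4.1.1).** A patient fails "If there is at least one record of" *P. aeruginosa* between 3 and 15 months. Evaluability for the later time point is set as follows: "they must have either a positive sample within the primary outcome window (3-15 months) or they must have a sample within 28 days either side" (counted around T15), so a patient with a positive needs no T15 sample. Patients who have not regrown the organism and "do not have a sample within the 15 month window (defined above) will not be included in the primary analysis". Of those withdrawn before 15 months, "they will only be included in the primary outcome analysis if they have failed". Section 17.1 rules out imputation.

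**Sensitivity analyses (SAP 19.1).**
- 19.1.1: "all patients who have been followed up past 3 months but not had a sample within the 15 month window will be assumed" not to have had the organism (success).
- 19.1.2: the same group "will be assumed to have had" it (failure).
- 19.1.3: patients followed for more than 15 months without a sample in the T15 window are brought in. "These patients will be classified as success or failure based on the next sample that was taken following the 15 month window".
- 19.1.4: a random centre effect, which does not address missing data.

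**The concern.** The primary analysis uses observed cases only, and its inclusion rule depends on the outcome: an early withdrawal counts if the patient has already failed and drops out otherwise. Sections 19.1.1 to 19.1.3 are the only checks on that rule, so their definitions matter.

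Two things could go wrong. If 19.1.1 and 19.1.2 both agree with the primary result, readers may conclude that it survives any plausible assumption about the missing patients, when only scenarios common to both arms were tried and early losses were left out. And if 19.1.1 disagrees, the cause may be that known failures were recoded, which says nothing about missing data.

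**Working it through.** **1. The rules applied to three types of patient**

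| Patient | Primary (17.4.1.1) | 19.1.1 | 19.1.2 | 19.1.3 |
|---|---|---|---|---|
| Positive at 6 months, no T15-window sample, next late sample negative | Failure | Success | Failure | Success |
| No positive, withdrawn between 3 and 15 months | Excluded | Success | Failure | Excluded |
| Lost before 3 months | Excluded | Excluded | Excluded | Excluded |

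Row 1 is the contradiction with 17.4.1.1. It affects 19.1.1 and 19.1.3 but not 19.1.2. Row 3 is the uncovered group.

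**2. Same outcome in both arms: the algebra**

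Let p1 and p2 be the success proportions among observed patients (IV, oral), with the same missing fraction m in each arm.
- All failure: RR = p1(1-m) / [p2(1-m)] = p1/p2, unchanged.
- All success: RR = [p1(1-m)+m] / [p2(1-m)+m], which moves toward 1 without crossing it.
- In both, the risk difference is (1-m)(p1-p2), so its sign cannot change.

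**3. Illustration**

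From the SAP: relative risk with a chi-squared test (17.4.1.2), two-sided 5% (Section 12), 1:1 allocation (8.7). The SAP leaves sample size to the protocol and gives no success or dropout rate, so there is no planned figure to reproduce. Assumed: 100 per arm, 10 missing per arm, all lost after 3 months, observed 54/90 v 40/90. P-values are from the uncorrected chi-squared test.

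| Analysis | IV v oral | RR | p |
|---|---|---|---|
| Complete case | 54/90 v 40/90 | 1.35 | 0.037 |
| 19.1.1 (no recoding of known failures) | 64/100 v 50/100 | 1.28 | 0.046 |
| 19.1.2 | 54/100 v 40/100 | 1.35 | 0.047 |
| Missing IV fail, missing oral succeed | 54/100 v 50/100 | 1.08 | 0.57 |
| Missing IV succeed, missing oral fail | 64/100 v 40/100 | 1.60 | 0.0007 |

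With about 60% v 45% observed success and other amounts missing, the assignment least favourable to IV gives:
- 5 missing per arm: 57/100 v 48/100, RR 1.19, p=0.20.
- 20 missing per arm: 48/100 v 56/100, RR 0.86, p=0.26, a reversed direction.

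**4. Unequal missingness**
- 15 IV v 5 oral missing: complete case p=0.048, 19.1.1 p=0.010, 19.1.2 p=0.26.
- 5 IV v 15 oral missing: p=0.040, 0.20 and 0.007.

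Here the planned pair does diverge.

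**5. Recoding known failures under the literal 19.1.1**

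Start from 64/100 v 50/100 (RR 1.28, p=0.046) and turn some documented failures into successes (assumed numbers):
- 5 IV and 5 oral: 69/100 v 55/100, RR 1.25, p=0.041.
- 5 IV and 10 oral: 69/100 v 60/100, RR 1.15, p=0.18.
- 5 IV and 15 oral: 69/100 v 65/100, RR 1.06, p=0.55.

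**6. Early losses**

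If 5 of the 10 missing per arm are lost before 3 months, 19.1.1 is 59/95 v 45/95 (RR 1.31) and 19.1.2 is 54/95 v 40/95 (RR 1.35). Under 19.1.1 the result sits closer to the complete-case 1.35 than the 1.28 in step 3, because those 5 per arm are never tested.

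**The case against.** **Intent.** Each of 19.1.1 to 19.1.3 starts from the derivation in 17.4.1.1, under which a positive at 3-15 months is a failure. The headings of 19.1.1 and 19.1.2 speak of withdrawn patients, the change log describes these analyses as widened to take patients in, and nobody needs to assume a result that is already on record. Recoding was probably not intended. That stands as a reading of intent. But the operative sentence cites the derivation and then departs from it for all patients in the stated group, and a programmer who follows it will recode.

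**Robustness.** A reader might infer that these analyses cannot test robustness to missing data at all, or that they will agree however fragile the result is. The SAP does not support that. The 19.1.1/19.1.2 pair can diverge when missingness differs by arm (working, step 4), and 19.1.3 uses each patient's observed later sample, not an outcome common to both arms. Nor do all three analyses overwrite failures, since 19.1.2 only assigns failure.

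**Convention.** All-success and all-failure form a recognised pair, and opposing assignments are extreme. That is fair, and it is why they should be read as bounds. Section 14.2 also allows further analyses after blind review, but the version that resulted contains no arm-specific one for the primary outcome.

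**Conclusion.** The point holds in a limited form. Sections 19.1.1 and 19.1.3 lack an exemption for documented failures and, read literally, contradict 17.4.1.1. Patients not followed past 3 months are in none of 19.1.1 to 19.1.3. No analysis lets the missing patients do better in one arm than in the other. The set therefore probes missing data in part but does not bound its effect.

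In the assumed example with 10 missing per arm, the two planned extremes span RR 1.28 to 1.35, against 1.08 to 1.60 under opposing assignments. These counts are illustrative. The SAP gives no success rate, no dropout and no count of failures without a T15-window sample, so neither the width of the bounds nor the share of patients recoded can be computed for this trial.

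**What to change.** 1. In 19.1.1 to 19.1.3, state that any patient with a positive sample at 3-15 months stays a failure, and that reclassification applies only to patients with no such positive and no sample in the T15 window.
2. Extend 19.1.1 and 19.1.2 to all randomised patients without a primary outcome, including those lost before 3 months. Section 19.1.3 can stay as it is in this respect, since it depends on a later sample.
3. Add the two opposing assignments (missing succeed in IV and fail in oral, and the reverse), or a tipping-point grid over arm-specific success among the missing.

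The cost is a few lines of SAP text and a few extra 2x2 tables. The opposing extremes will be wide and should be reported as bounds, not as plausible estimates; the grid is the more informative choice if missingness is appreciable.

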#### 19.1.2 Withdrawn patients all classified as failure

Derivation and analysis as in Section 17.4.1.1 and Section 17.4.1.2 but all patients who have been followed up past 3 months but not had a sample within the 15 month window will be assumed to have had *P. Aeruginosa*.

#### 19.1.3 Results of blind review

Derivation and analysis as in Section 17.4.1.1 and Section 17.4.1.2 but all patients that have been followed up for more than 15 months but not had a sample within the 15 month window will be included. These patients will be classified as success or failure based on the next sample that was taken following the 15 month window.

#### Form prepared: 20/06/2018 v1.0 for TORPEDO-CF Study

Page 43 of 47

#### 19.1.4 Investigation of heterogeneity across sites

A logistic regression model adjusted for centre as a random effect will be fitted to investigate heterogeneity across sites.

#### **19.2 Additional analyses of secondary outcomes**

#### 19.2.1 Sensitivity analysis: Time to reoccurrence of original P.aeruginosa infection

Derivation as in Section 17.4.2.1.1 but  $T_0$  amended to be date of treatment commencement rather than date of randomisation. Analysis as in Section 17.4.2.1.2.

#### **19.2.2** Time to first pulmonary exacerbation

#### 19.2.2.1 Derivation

Derivation of pulmonary exacerbation as outlined in Section 17.4.2.6.1. Patients will be categorised with a censoring indicator variable E:

E = 0: no visits for which  $PE_{score} > 2.6$ ; or

1: there was at least one visit during follow-up for which  $PE_{score} > 2.6$ .

A time to event (T) in months will be calculated for each patient as  $T = T_1 - T_0$ , where

T0 = date of first treatment (CRF: *Treatment CRF*, variable: TATRDTD for patients on IV treatment, OCDTCPSD for patients on oral treatment)

If E=0:

T1 = date of last available follow-up (CRF: *Follow-up*, variable: FUVISITD)

If E=1:

 $T_1$  = first visit date which indicates E=1 (CRF: *Follow-up*, variable: FUVISITD).

#### 19.2.2.2 Analysis

The time-to-first exacerbation in each treatment arm will be presented using Kaplan-Meier curves. The log-rank test will be used to test for a difference between treatment groups.

#### 19.2.3 At least one exacerbation during a time period

#### 19.2.3.1 Derivation

Derivation of pulmonary exacerbation as outlined in Section 17.4.2.6.1. For time-period  $T_A$  to  $T_B$ , ( $T_{AB}$ ) a binary outcome variable  $X_{AB}$  will be derived:

 $X_{AB}=0$  if for all visits during  $T_{AB}$ , E=0.

 $X_{AB}=1$  if for at least one visit during  $T_{AB}$ , E=1.

Time periods of interest are treatment phase (1st 3 months), first year after treatment (3-15 months post randomisation) and the remainder of follow-up (15-24 months post randomisation).

#### 19.2.3.2 Analysis

The number and percentage of participants having had at least one exacerbation during the treatment phase, during the first year after treatment, and during the 2nd year after treatment will be presented. Denominators for percentages will be the number of patients followed up during the time-period within treatment arm, in preference to the number randomised.

## **20 Safety Evaluations**

#### 20.1 Data sets analysed

The safety analysis data set will contain all participants that are randomised and commenced treatment.

Only AEs in line with reporting timelines in the protocol (from commencement of allocated treatment (IMP & NIMP) until 28 days after cessation of allocated treatment) will be presented. Versions 1.0-5.0 of the protocol required all SAEs to be reported as such.

#### **20.2 Presentation of the data**

All events will be MedDRA coded. The classifications will be presented in a table. The number of occurrences of each AE (at the preferred term and system organ class levels) and the number (and percentage) of patients experiencing each AE will be presented for each treatment arm and overall. A similar table will be produced for all SAEs reported under all versions of the protocol.

A cross-tabulation of AE severity by 'relationship to study drug' will be presented by treatment group and overall.

Each SAE reported under versions 1.0-5.0 of the protocol and each SAR reported under version 6.0 of the protocol onwards will be presented in the form of line listings detailing:

- SAE number
- Treatment
- Preferred term
- System organ class
- Date of onset
- Serious criteria (reporting of all that apply from 7 possible options) [PI and CI assessment]
- Severity (Mild / Moderate / Severe) [PI assessment]
- Relationship to study drug [PI and CI assessment]

- Expectedness [CI assessment]
- Most likely cause (Disease under study / Other illness / Prior or concomitant treatment / Protocol procedure / Lack of efficacy) [PI assessment]
- Outcome

For the purposes of reporting to EUDRACT, a table including only non-serious AEs will also be presented. This will report the number of occurrences of each AE (at the preferred term and system organ class levels) and the number (and percentage) of patients experiencing each AE, for each treatment arm and overall. No formal statistical testing will be undertaken.

